Adverse events and concomitant medications will be monitored throughout the study.

Follow Up Period (4 weeks after EOT± allowed windows)

Follow-up visit (V18) will be performed at 4 weeks after the End of Treatment (EOT) visit. The following assessments will be performed at V18: vital signs, physical examination, pulse oxygen saturation, blood sample collection for immunophenotypic biomarker analysis, assessment for the requirement of hospitalization, review of adverse events and concomitant medications.

Note: During visits conducted at the study clinic, subjects and site personnel will use appropriate protective gear (e.g., masks, gloves) to prevent the spread of the infection.

Duration of Treatment:

Screening Period (Screening to Baseline): Up to 7 days (1 Week)

Treatment Period: 56 Days

Follow-Up Period: 28 Days (4 weeks)

Total Study Duration: 91 Days

Inclusion Criteria:

- 1. Male or female adult \geq 18 years of age at time of enrollment.
- 2. Prior confirmed COVID-19 diagnosis by standard RT-PCR assay or equivalent testing
- 3. Clinical Symptom Score of ≥6 AND at least two symptoms of moderate or higher severity as listed below at the time of Screening and currently experiencing two or more of the following symptoms consistent with COVID-19 infection for a prolonged period of time (>12 weeks).

Clinical symptoms include the following:

- Respiratory symptoms such as cough, sore throat, stuffy or runny nose, shortness of breath (difficulty breathing), tightness of chest..
- Neurological symptoms such as difficulty in concentration (brain fog), sleep disturbance/insomnia, headache, dizziness, anxiety, tingling or numbness, loss of sense of smell or taste.
- Cardiovascular and Gastrointestinal symptoms such as feeling of fast heartbeat, nausea, vomiting, diarrhea.

CONFIDENTIAL Page 9 of 101

Name of Sponsor/Company:		
CytoDyn, Inc.		
Name of Study Product:		
Leronlimab (PRO 140)		
Protocol Number: Indication:		
CD15_COVID-19	Coronavirus Disease 2019 (COVID-19)	

- Musculoskeletal symptoms such as muscle aches/cramps, muscle weakness, joint pain/swelling.
- General immune response symptoms such as fatigue (low energy or tiredness), chills or shivering, feeling hot or feverish, or exertional malaise (feeling of discomfort, illness, or lack of well-being after physical activity or mental stress).

Note: Clinical Symptom Score is obtained from the patient diary (refer to Appendix 1 for scoring instructions).

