4. Electrocardiogram (ECG) with no clinically significant findings as assessed by the Investigator.

Note: Below are the examples of clinically significant and non-clinically significant ECG abnormalities:

- ECG findings indicative of acute myocardial infarction or acute ischemic changes would be considered clinically significant abnormalities.
- ECG finding such as atrial fibrillation, atrial flutter, paced rhythms in individuals who have undergone permanent pacemaker placement, evidence of prior infarction, unchanged stable conduction abnormalities e.g. right bundle branch block, or any other finding which does not significantly impact mortality would be considered non-clinically significant findings and subjects with these abnormal findings would be allowed to enroll in the study.
- 5. Subject (or legally authorized representative) provides written informed consent prior to initiation of any study procedures.
- 6. Men and women of childbearing potential and their partner must agree to use two medically accepted methods of contraception (e.g., barrier contraceptives [male condom, female condom, or diaphragm with a spermicidal gel], hormonal contraceptives [implants, injectables, combination oral contraceptives, transdermal patches, or contraceptive rings], or one of the following methods of birth control (intrauterine devices, bilateral tubal occlusion, or vasectomy) or must practice complete sexual abstinence for the duration of the study (excluding women who are not of childbearing potential and men who have been sterilized).
- 7. Females of child-bearing potential must have a negative urine pregnancy test at Screening Visit and prior to receiving the first dose of study drug; and Male participants must agree to use contraception and refrain from donating sperm for at least 90 days after the last dose of study intervention.
- 8. Subject is willing and able to comply with scheduled visits, drug administration plan, laboratory tests, other study procedures and study restrictions

Exclusion Criteria:

Exhibiting signs of moderate or severe pulmonary disease (such as COPD, asthma, or pulmonary fibrosis)

CONFIDENTIAL Page 10 of 101

Name of Sponsor/Company:		
CytoDyn, Inc.		
Name of Study Product:		
Leronlimab (PRO 140)		
Protocol Number: Indication:		
CD15_COVID-19	Coronavirus Disease 2019 (COVID-19)	

- 2. Ongoing requirement of oxygen therapy
- 3. Pulse oxygen saturation (SpO2) of <94% on room air at the time of screening
- 4. History of splenectomy

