1.6. RISKS / BENEFITS ASSESSMENT

Allergic Reaction

Leronlimab (PRO 140) belongs to the monoclonal antibody class of drugs. Monoclonal antibodies are sometimes associated with allergic reactions or flu-like reactions (such as fever, chills, and aches) or injection-site reactions. These events are usually of short duration if they occur at all. Severe allergic reactions, however, can be life-threatening. Although anaphylaxis has not been observed in prior trials of leronlimab (PRO 140), the protein infusion always carries theoretical risk for anaphylactic shock. Accordingly, whenever leronlimab (PRO 140) is administered to subjects, procedures should be available and in place to manage the occurrence of anaphylactic shock.

Immune Response

People who take leronlimab (PRO 140) or other monoclonal antibodies can also develop an immune response to leronlimab (PRO 140) that may affect their ability to receive monoclonal antibodies, or to benefit from diagnosis or therapy with a monoclonal antibody in the future.

Pregnancy

Risks to unborn babies exposed to leronlimab (PRO 140) are unknown at this time; thus pregnant females will be excluded from this study. Females of childbearing potential must have a negative pregnancy test prior to enrollment. Both male and female patients and their partners of childbearing potential must agree to use appropriate birth control methods throughout the study duration (excluding women who are not of childbearing potential and men who have been sterilized).

Venipuncture

Blood sampling is required as part of the study protocol. Blood sampling carries a minimal risk of minor discomfort and the possibility of minor bruising at the site of the needle puncture and, rarely, the possibility of infection at the needle puncture site.

Unknown Risks

As with all research, there is the remote possibility of risks that are unknown or that cannot be foreseen based on current information.

Theoretical risk for increased severity of West Nile virus infection

Individuals who lack a functional CCR5 gene are at increased risk for severe infection by West Nile virus [Thompson, 2009]. Because of this, treatment with CCR5 co-receptor antagonists poses a theoretical risk for increased severity of West Nile virus infection. However, this concern is mitigated by several factors. First, no increased risk was observed for individuals who possess one functional and one non-functional CCR5 gene, indicating that an intermediate amount of

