5.3. REMOVAL OF SUBJECTS FROM STUDY TREATMENT AND/OR STUDY AS A WHOLE

Subjects can be taken off the study treatment and/or study as a whole at any time at their own request, or they may be withdrawn at the discretion of the investigator for safety, behavioral or administrative reasons. In the case that a subject is removed from the study due to safety reasons, the FDA and other global regulatory authority will be notified. The reason(s) for discontinuation must be clearly documented on the appropriate eCRF and may include:

- Subject voluntarily withdraws from treatment (follow-up permitted)
- Subject withdraws consent (no follow-up permitted)
- Subject is unable to comply with protocol requirements

CONFIDENTIAL Page 54 of 101

- Subject experiences unacceptable toxicity
- Treating physician determines that continuation on the study would not be in the subject's best interest
- Subject becomes pregnant
- Subject becomes lost to follow-up (LTF)
- Subject will be withdrawn from the study if 2 consecutive doses of study drug are missed
- Subject manifesting Grade 4 or Grade 3 toxicity attributable to the Leronlimab (PRO 140)

If a subject fails to return for the scheduled study visit or is discontinued from the study, an attempt will be made to determine the reason(s). If the subject is unreachable by telephone, a registered letter will be sent to the subject requesting that he/she contact the clinic.

All patients with an ongoing SAE or AE attributable (definitely, probably, or possibly related) to the study treatment at the Post-Study (Follow-up) Visit (scheduled or premature) must be followed until the event is resolved (with or without sequelae) or deemed stable.

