2.3 Study Duration

A subject will be in this trial at maximum of around 91 Days.

• Screening Period (Screening to Baseline): Up to 7 days (1 Week)

• Treatment Period: 56 Days

• Follow-up Phase: 28 Days (4 weeks)

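### Contraception for women of childbearing potential is tied to study duration, with no period counted from the last dose, so its length is unclear for a woman who leaves early

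*Combined protocol and SAP*

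**What the plan says.** Inclusion criterion 6, worded alike in the synopsis and Section 3.3.1, asks men and women of childbearing potential and their partners to use two accepted methods, or one of a short list of long-acting methods, or else they "must practice complete sexual abstinence for the duration of the study". In that sentence the time phrase may attach only to abstinence. Section 1.6 is clearer: patients and partners "must agree to use appropriate birth control methods throughout the study duration". The same section gives the reason: "Risks to unborn babies exposed to leronlimab (PRO 140) are unknown at this time".

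Only men have a period counted from dosing. Inclusion criterion 7 states that "Male participants must agree to use contraception and refrain from donating sperm for at least 90 days after the last dose of study intervention". The one post-dose period that reaches women is in Section 9.5, which asks for notification of a pregnancy arising within 30 days of the last dose. That is a reporting duty.

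The synopsis gives "Total Study Duration: 91 Days". SAP Section 2.3 says "A subject will be in this trial at maximum of around 91 Days".

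On early exit, Section 5.3 says "Subjects can be taken off the study treatment and/or study as a whole at any time at their own request" and also "Subject will be withdrawn from the study if 2 consecutive doses of study drug are missed". It separates stopping treatment with follow-up allowed from withdrawing consent with none allowed, and it mentions a premature follow-up visit. Section 4.2.4 treats the last treatment-phase visit as the end-of-treatment (EOT) visit, which includes a urine pregnancy test. Section 4.3 places follow-up 28 (±3) days after EOT.

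**The concern.** Fetal exposure depends on the time since the last dose, not on enrolment status. A rule tied to study duration works for a woman who stays to the end, because the follow-up visit falls well after her last injection. It is less certain for a woman who leaves. If study duration means her own time in the study, her undertaking could lapse within days of an injection. The protocol describes the fetal risk as unknown and relies on contraception to control it. The Section 9.5 duty still applies to her, but it takes effect only after a pregnancy has occurred.

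The protocol's own data suggest that drug effect is likely still present at such an exit. Section 1.4.2.5 reports high receptor occupancy for 29 days after single intravenous doses of 5 and 10 mg/kg in HIV-infected adults. Section 1.4.1 gives an elimination half-life of about 200 hours in monkeys. Neither is direct evidence for weekly 700 mg subcutaneous dosing.

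**Working it through.** **Inputs.** Screening up to 7 days, treatment 56 days, follow-up 28 days (synopsis). Eight weekly doses, V2 (Day 0) to V16 (Day 49), with a ±1 day window on each weekly visit. V17 (EOT) at 7 (±1) days after V16 and V18 at 28 (±3) days after V17. Withdrawal from the study after two consecutive missed doses (Section 5.3).

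**The plan's figure.** 7 + 56 + 28 = 91 days, which matches the synopsis. Counted from the first dose, 91 − 7 = Day 84, the nominal day of V18.

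**Completers.** V16 to V18 is (7 ± 1) + (28 ± 3), so 6 + 25 = 31 to 8 + 31 = 39 days after the last dose.

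**Early leavers, reading (a): a fixed 91-day schedule.** The duty runs to Day 84 whenever she leaves.
- Last dose anywhere from Day 0 to Day 49: 84 − 49 = 35 to 84 − 0 = 84 days.
- Two missed doses, so last dose no later than Day 35: 84 − 35 = 49 to 84 days.

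**Reading (b): she permits follow-up, with an EOT visit and a follow-up visit 28 (±3) days later.**
- If her last dosing visit counts as EOT: 25-31 days after the last dose.
- If EOT falls at exit after two missed doses (day 15-16, derived below): 15 + 25 = 40 to 16 + 31 = 47 days.

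**Reading (c): the duty ends on exit.**
- Two missed weekly doses, counted when the second window closes: 7 + 8 = 15 days (first missed visit at its nominal day) to 8 + 8 = 16 days (both at the late edge).
- Consent withdrawn before the next weekly dose: 0 to 7 + 1 = 8 days.

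**Compared with 30 days.** The protocol sets no minimum contraception period for women, so the Section 9.5 notification window is used only as a reference.

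| Reading | Days after last dose | Short of 30 |
|---|---|---|
| Completer | 31-39 | none |
| (a) Fixed schedule | 35-84 | none |
| (b) Last dosing visit counts as EOT | 25-31 | 0-5 |
| (b) EOT at exit after two missed doses | 40-47 | none |
| (c) Two missed doses | 15-16 | 14-15 |
| (c) Consent withdrawn before next dose | 0-8 | 22-30 |

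**Residual drug, illustrative only.** Fraction remaining = 2^(−hours/200), using the monkey half-life: 0.287 at 15 days (360 h), 0.264 at 16 days (384 h), 0.083 at 30 days (720 h).

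**Number affected.** Half of 50 is 25 on leronlimab. Assume that 30-60% are women of childbearing potential and 10-20% leave early; neither rate is in the documents. Then 25 × 0.3 × 0.1 = 0.75 to 25 × 0.6 × 0.2 = 3, or about 1-3 women leaving early. This does not count pregnancies.

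**The case against.** The strongest reply is that the protocol itself states a total study duration of 91 days, so Section 1.6 is most naturally read as a fixed period, under which nobody falls short. The contrary text is in the SAP, which imposes no contraception duty, and its reference to a maximum may reflect only that screening can take up to 7 days. Sections 4.2.4, 4.3 and 5.3 also point to an EOT visit and later follow-up for early leavers who allow it. Pregnancy tests at V1, V2, V10 and V17 and the Section 9.5 notification duty are further controls. The 30-day yardstick is borrowed, and the largest shortfall concerns consent withdrawal, where the site can check nothing.

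Much of this stands. It removes the gap under reading (a) and reduces it to 0-5 days under reading (b). It does not settle which reading applies. No text explicitly requires V18 of withdrawn subjects, and completion (Section 5.1) is defined only for those who finish all follow-up assessments. A woman told that she has been withdrawn from the study could reasonably conclude that a duty set for the study's duration is over.

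A reader might go further and infer that the plan leaves women unprotected after dosing, or that they need the same 90 days as men. The documents do not support either. Completers have 31-39 days of cover, and nothing in the text sets 90 days, or any other figure, as the minimum for women.

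**Conclusion.** The point holds as a gap in wording for early leavers. The contraception rule for women has no anchor to the last dose, and three tenable readings give cover from 0 to 84 days. A shortfall of 14-15 days (two missed doses) or 22-30 days (consent withdrawal) arises on only one of the three, and only against a borrowed 30-day reference.

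It would be tempting to conclude that participants are in fact told they may stop contraception on exit. That cannot be shown: the consent form was not available for this review and may already state a period. The number affected rests on assumed rates, and the evidence on residual drug is indirect. Low priority, but cheap to improve.

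**What to change.** In inclusion criterion 6 (synopsis and Section 3.3.1) and Section 1.6, require women of childbearing potential to use contraception through the study and for at least 30 days after the last dose, whichever is longer, regardless of early withdrawal. Align the consent form if it does not already say so. The 30 days matches the Section 9.5 window.

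The cost is one sentence in each place. No visit, test or reporting duty is added, and nothing changes for completers. The downside is a somewhat longer undertaking for early leavers, which the site cannot check once consent is withdrawn. A longer period, such as the men's 90 days, is an optional sponsor choice. It would extend the commitment of every completing woman of childbearing potential, and lengthening the Section 9.5 window to match would create a reporting duty after V18, the last scheduled contact.

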CNS	Central Nervous System
COVID-19	Coronavirus Disease 2019
CRF	Case Report Form
CRO	Contract Research Organization
CS	Clinically Significant
CTCAE	Common Terminology Criteria for Adverse Events
eCRF	Electronic Case Report Form
CV	Curriculum Vitae
DSMC	Data Safety Monitoring Committee
ECG	Electrocardiogram
EOT	End of Treatment
FDA	U.S. Food and Drug Administration
FDP	Finished Drug Product
FUV	Follow-up Visit
GCP	Good Clinical Practice
GFR	Glomerular Filtration Rate
GMP	Good Manufacturing Practice
HEENT	Head, Ears, Eyes, Nose, and Throat
HIPAA	Health Insurance Portability Accountability Act
HIV	Human Immunodeficiency Virus
IA	Interim Analysis
IC	Inhibitory Concentration
ICF	Informed Consent Form
ICH	International Conference on Harmonization

CONFIDENTIAL Page 20 of 101

Abbreviation	Term
ICU	Intensive Care Unit
IEC	Independent Ethics Committee
IND	Investigational New Drug
IP	Investigational Product
IRB	Institutional Review Board
ISR	Injection Site Reaction
ITT	Intent to Treat
IV	Intravenous
IWRS	Interactive Web Based Response System
LAR	Legally Authorized Representative
LTF	Lost to Follow-Up
MedDRA	Medical Dictionary for Regulatory Activities
mg	Milligram
MTD	Maximum Tolerated Dose
NEWS	National Early Warning Score 2
OBT	Optimized Background Therapy
PD	Pharmacodynamic
PK	Pharmacokinetic
PI	Principal Investigator
SAE	Serious Adverse Event
SARS-CoV-2	Severe Acute Respiratory Syndrome Coronavirus 2
SC	Subcutaneous
SOP	Standard Operating Procedure
SpO_2	Peripheral Capillary Oxygen Saturation
SV	Screening Visit
TEAE	Treatment Emergent Adverse Event
TNBC	Triple Negative Breast Cancer
Treg	T regulatory cell
V	Visit
VL	Viral Load

CONFIDENTIAL Page 21 of 101

1 INTRODUCTION AND BACKGROUND

1.1. STATEMENT OF INTENT

The design, conduct and reporting of this study shall be conducted in compliance with the protocol, International Conference on Harmonization/Good Clinical Practice (ICH/GCP), and all appropriate regulatory requirements. Investigator(s) participating in this study will have documented training in GCP. Independent monitoring of the trial will be accomplished utilizing a Contract Research Organization (CRO).

1.2. BACKGROUND OF THE DISEASE

Severe acute respiratory syndrome coronavirus 2 (SARS-CoV-2), the viral cause of coronavirus disease 2019 (Covid-19) was first identified in late 2019 in Wuhan, Hubei province, China. On 11 March 2020, the World Health Organization declared the disease a global pandemic. The global burden of SARS CoV-2 infection continues to increase with estimates of more than 37 million people infected and over one million deaths as of October 2020.

While some individuals infected with SARS-CoV-2 may be asymptomatic, the majority of people display symptomatic disease varying from mild to critical in severity. Severe-to-critical illness is typically marked by hypoxemic respiratory failure requiring ventilatory support. Morbidity and mortality rates are elevated among patients with pre-existing co-morbidities such as cardiovascular disease, diabetes mellitus, chronic respiratory disease, hypertension and cancer. The observed case fatality ratio (CFR) varies considerably from country to country and over time. However, the CFR in the USA has been estimated at 2.8%. While public discourse on COVID-19 has largely centered around patients with severe or fatal illness, it has become apparent that a growing number of patients experience mild to moderate symptoms for a prolonged period of time.

A patients and survivors of COVID-19 from the Body Politic COVID-19 Support Group created and analyzed a survey targeted at patients experiencing symptoms for over two weeks. Responses from 640 patients were collected between April 21 and May 2, 2020 (https://patientresearchcovid19.com/research/report-1/).

Key findings were symptoms are not limited to cough, fever, and shortness of breath. Other widely reported symptoms span neurological, gastrointestinal, cardiovascular, and other systems and include fatigue (reported by 81.3% of respondents), chills/sweats (75.9%), body aches (73.9%), headache (72.2%), brain fog and concentration issues (68.6%), gastrointestinal issues (66.9%), trouble sleeping (66.1%), and dizziness (60.6%). An elevated temperature under 100.1°F was reported by 72.2% of respondents while a fever over 100.1°F was reported by only 47.8% of respondents. The other key finding was recovery is volatile, includes relapses, and can take six or more weeks. At the time respondents took the survey, 90.6% reported not being recovered and were, on average, on day 40 of experiencing symptoms. 89% of respondents said that their

CONFIDENTIAL Page 22 of 101

symptoms fluctuated in intensity and frequency, and 70% reported new symptoms appearing at different stages of their illness. Based on textual responses and anecdotes from the support group, patients may feel better for days or weeks only to relapse into old or new symptoms soon after.

The aim of this study is to test efficacy and safety of leronlimab (PRO140) for treatment of adult patients with prolonged symptoms of Coronavirus disease 2019 (COVID-19).

1.3. LERONLIMAB (PRO 140)

Leronlimab (PRO 140) is a humanized IgG4,κ monoclonal antibody (mAb) to the C-C chemokine receptor type 5 (CCR5), under development as a therapy for human immunodeficiency virus (HIV) infection, Coronavirus disease 2019 (COVID-19), cancer, and other diseases, including Graft versus host disease (GVHD) and Nonalcoholic steatohepatitis (NASH).

Leronlimab (PRO 140) has been administered intravenously or subcutaneously to more than 1000 patients across multiple studies. Leronlimab has been generally well-tolerated and no patterns of drug-related toxicities have been observed.

1.4. SUMMARY OF PRIOR PRE-CLINICAL AND CLINICAL STUDIES

1.4.1. Pre-Clinical Studies with PRO 140

In vitro and *in vivo* preclinical studies have been conducted to determine the pharmacokinetic, immunogenicity, and toxicity profiles of leronlimab (PRO 140) following IV and SC administration. Several acute and chronic toxicity studies have been conducted to support the clinical development plan.

Acute toxicity of leronlimab (PRO 140) was evaluated in New Zealand rabbits, following IV administration of 5 or 15 mg/kg. Chronic toxicity was evaluated in cynomolgus monkeys following biweekly administration of IV doses up to 10 mg/kg for six months and biweekly administration of various SC doses up to 50 mg/kg for 24 weeks. The drug was generally well tolerated. Biweekly administration of IV doses up to 10 mg/kg for six months resulted in minimum to mild lymphoid hyperplasia in assorted lymph nodes and spleen, which was considered an expected immune response to a foreign protein. Biweekly administration of SC doses up to 50 mg/kg for 24 weeks resulted in minimum injection-site reactions (minimal, multifocal, mononuclear cell infiltrates in the subcutis), which were considered due to an inflammatory response to the injected antigen. Monkeys tolerated treatment with leronlimab (PRO 140) for 24 weeks without evidence of local or systemic toxicity. Leronlimab (PRO 140) caused no mortality, cageside observations, in-life injection-site observations, or gross pathologic findings. Chronic treatment with leronlimab (PRO 140) did not affect body weight, food consumption, hematology, clinical chemistry or coagulation parameters.

CONFIDENTIAL Page 23 of 101

Both IV and SC administration resulted in elimination half-lives of approximately 200 hours, and overall exposure increased with increasing doses. Following SC administration of leronlimab (PRO 140) in monkeys, the maximal concentration (C_{max}) was achieved within 56 hours and bioavailability for leronlimab (PRO 140) after SC dosing was approximately 70%.

1.4.2. Clinical Studies with PRO 140

Current human experience with leronlimab (PRO 140) consists of ten completed and nine ongoing clinical trials, mostly on healthy subjects or HIV-1 positive subjects. These studies are summarized in Table 1-1 and Table 1-2. In all clinical trials, the majority of adverse events (AEs) have been mild or moderate. No dose-limiting toxicities or patterns of drug-related toxicities were observed. Antiviral activity was potent, rapid, prolonged, dose-dependent, and highly significant.

